### **9.2.2 SAE reporting**

To ensure patient safety, every SAE, regardless of causality, occurring after the subject has provided informed consent and until 30 days after the patient has stopped study participation (defined as time of last dose of study drug taken or last visit whichever is the later) must be reported to Novartis within 24 hours of learning of its occurrence as described below. Any SAEs experienced after this should only be reported to Novartis if the investigator suspects a causal relationship to study treatment.

Recurrent episodes, complications, or progression of the initial SAE must be reported as follow-up to the original episode, regardless of when the event occurs. This report must be submitted within 24 hours of the investigator receiving the follow-up information. An SAE that is considered completely unrelated to a previously reported one should be reported separately as a new event.

Information about all SAEs (either initial or follow up information) is collected and recorded on the paper Serious Adverse Event Report Form. The investigator must assess the relationship to each specific component of study treatment (if study treatment consists of several drugs) complete the SAE Report Form in English, and send the completed, signed form by fax within 24 hours after awareness of the SAE to the local Novartis Drug Safety and Epidemiology Department, notifying the Study Lead. Contact information is listed in the Site Operations Manual.

The original copy of the SAE Report Form and the fax confirmation sheet must be kept with the source documentation at the study site. Follow-up information should be provided using a new paper SAE Report Form stating that this is a follow-up to a previously reported SAE.

SAEs (initial and follow-up) that are recorded electronically in the Electronic Data Capture system should be entered, saved and e-signed within 24 hours of awareness of the SAE or changes to an existing SAE. These data will automatically be submitted to Novartis Drug Safety & Epidemiology immediately after investigator signature or 24 hours after entry, whichever occurs first. Study site personnel must also inform the Study Lead.

Follow-up information provided should describe whether the event has resolved or continues, if and how it was treated, whether the treatment code was broken or not and whether the subject continued or withdrew from study participation. Each re-occurrence, complication, or progression of the original event should be reported as a follow-up to that event regardless of when it occurs.

If the SAE is not previously documented in the Investigator's Brochure (new occurrence) and is thought to be related to the investigational treatment a Drug Safety and Epidemiology Department associate may urgently require further information from the investigator for Health Authority reporting. Novartis may need to issue an Investigator Notification (IN) to inform all investigators involved in any study with the same investigational treatment that this SAE has been reported. Suspected Unexpected Serious Adverse Reactions (SUSARs) will be collected and reported to the competent authorities and relevant ethics committees in accordance with EU Guidance 2011/C 172/01 or as per national regulatory requirements in participating countries.

### **9.3 Liver safety monitoring**

To ensure subject safety and enhance reliability in determining the hepatotoxic potential of an investigational drug, a standardized process for identification, monitoring and evaluation of liver events has to be followed.

The following two categories of abnormalities / adverse events have to be considered during the course of the study:

- Liver laboratory triggers, which will require repeated assessments of the abnormal laboratory parameter
- Liver events, which will require close observation, follow-up monitoring and completion of the standard base liver CRF pages

Please refer to [Table 9-1](#) for complete definitions of liver laboratory triggers and liver events.

Every liver laboratory trigger or liver event should be followed up by the investigator or designated personal at the trial site, as summarized below and detailed in in [Table 9-1](#).

For the liver laboratory trigger:

- Repeating the LFT within the next week to confirm elevation.

Repeat laboratory tests should be entered on the appropriate unscheduled local laboratory CRF page.

- If the elevation is confirmed, close observation of the patient will be initiated, including consideration of treatment interruption if deemed appropriate.

For the liver events:

- Repeating the LFT to confirm elevation as appropriate
- Discontinuation of the investigational drug (refer to [Section 7.1](#), if appropriate)
- Hospitalization of the subject if appropriate
- A causality assessment of the liver event via exclusion of alternative causes (e.g. disease, co-medications)
- An investigation of the liver event which needs to be followed until resolution.

These investigations can include serology tests, imaging and pathology assessments, hepatologist’s consultancy, based on investigator’s discretion. All follow-up information, and the procedures performed should be recorded as appropriate in the CRF, including the liver event overview CRF pages.

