## 2 Study objectives

### 2.1 Primary objective(s)

Primary objective(s)	Endpoints related to primary objective(s)

To determine the safety and tolerability of an 18-hour i.v. infusion of CLR325 in stable heart failure patients.

	

Frequency of adverse events in CLR325 treated patients as compared to patients treated with placebo.

Frequency of clinically significant changes in hematology or clinical chemistry laboratories or changes in blood pressure or heart rate.

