### **6.2 Treatment arms**

Patients will be assigned to one of the following 2 treatment arms in fixed randomization ratio (CLR325:Placebo):

- Single dose of CLR 325 (i.v.)
- Single dose of Placebo (i.v.)

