# **7 Discontinuation and study completion**

## **7.1 Discontinuation of study treatment**

Patients may voluntarily discontinue study treatment for any reason at any time.

The investigator must discontinue study treatment for a given patient if, on balance, he/she believes that continuation would be detrimental to the patient's well-being.

Study treatment must be discontinued under any of the following circumstances:

- Patient withdraws consent
- Any protocol deviation that results in a significant risk to the subject's safety
- Emergence of the following adverse events:
  - Acute myocardial infarction
  - Worsening myocardial ischemia
  - Sustained atrial or ventricular tachycardia
  - AICD discharge or anti-tachycardia pacing by the AICD in a patient with an AICD in place
  - An increase in non-sustained ventricular tachycardia or ventricular ectopy deemed clinically concerning by the investigator
  - Severe allergic reaction (e.g., angioedema)
- Occurrence of persistent elevation of systolic blood pressure to >180 mmHg or diastolic blood pressure >100 mm Hg
- Occurrence of symptomatic hypotension requiring persistent medical intervention (i.e. fluid replacement or inotropic therapy). Note that change of patient position does not qualify as an intervention if the need for this change in position is not persistent
- A drop in cardiac index of > 30% as compared to the average of all cardiac index measurements obtained prior to the start of infusion. All cardiac index values showing a 30% drop from baseline should be repeated and study drug terminated only if values are confirmed.
- Any clinically significant cardiac arrhythmia resulting in hemodynamic instability or requiring medical intervention to terminate
- Any of the following laboratory abnormalities:
  - Elevation in white blood cell count to greater than 2.5x above the ULN
  - Elevated AST or ALT > 8x above the ULN
  - Elevated AST or ALT > 3x above the ULN and TBL > 2x the ULN but without an increase in ALP to >2x the ULN
  - Elevated AST or ALT > 3x above the ULN and symptoms of malaise, fatigue, abdominal pain, nausea, vomiting, or rash with eosinophilia.

The appropriate personnel from the site and Novartis will assess whether study treatment should be discontinued for any patient whose treatment code has been broken inadvertently for any reason.

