**Table 9-1 Liver Event and Laboratory Trigger Definitions**

	Definition/ threshold
Liver laboratory triggers	3 x ULN < ALT / AST < 5 x ULN 1.5 x ULN < TBL < 2 x ULN
Liver events	ALT or AST > 5 x ULN ALP > 2 x ULN (in the absence of known bone pathology) TBL > 2 x ULN (in the absence of known Gilbert syndrome) ALT or AST > 3 x ULN and INR > 1.5 Potential Hy’s Law cases (defined as ALT or AST > 3 x ULN and TBL > 2 x ULN [mainly conjugated fraction] without notable increase in ALP to > 2 x ULN) Any clinical event of jaundice (or equivalent term) ALT or AST > 3 x ULN accompanied by (general) malaise, fatigue, abdominal pain, nausea, or vomiting, or rash with eosinophilia Any adverse event potentially indicative of a liver toxicity *

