**Table 9-2 Follow Up Requirements for Liver Events and Laboratory Triggers**

Criteria	Actions required	Follow-up monitoring
Potential Hy's Law case a	
 
Discontinue the study drug immediately
 
Hospitalize, if clinically appropriate
 
Establish causality
 
Complete liver CRF
 
	ALT, AST, TBL, Alb, PT/INR, ALP and $\gamma$ GT until resolution c (frequency at investigator discretion)
ALT or AST		
> 8 × ULN	
 
Discontinue the study drug immediately
 
Hospitalize if clinically appropriate
 
Establish causality
 
Complete liver CRF
 
	ALT, AST, TBL, Alb, PT/INR, ALP and $\gamma$ GT until resolution c (frequency at investigator discretion)
> 3 × ULN and INR > 1.5	
 
Discontinue the study drug immediately
 
Hospitalize, if clinically appropriate
 
Establish causality
 
Complete liver CRF
 
	ALT, AST, TBL, Alb, PT/INR, ALP and $\gamma$ GT until resolution c (frequency at investigator discretion)
> 5 to ≤ 8 × ULN	
 
Repeat LFT within 48 hours
 
If elevation persists, continue follow-up monitoring
 
If elevation persists for more than 2 weeks, discontinue the study drug
 
Establish causality
 
Complete liver CRF
 
	ALT, AST, TBL, Alb, PT/INR, ALP and $\gamma$ GT until resolution c (frequency at investigator discretion)
> 3 × ULN accompanied by symptoms b	
 
Discontinue the study drug immediately
 
Hospitalize if clinically appropriate
 
Establish causality
 
Complete liver CRF
 
	ALT, AST, TBL, Alb, PT/INR, ALP and $\gamma$ GT until resolution c (frequency at investigator discretion)
> 3 to ≤ 5 × ULN (patient is asymptomatic)	
 
Repeat LFT within the next week
 
If elevation is confirmed, initiate close observation of the patient
 
	Investigator discretion Monitor LFT within 1 to 4 weeks

Criteria	Actions required	Follow-up monitoring
ALP (isolated)		

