> 2 × ULN (in the absence of known bone pathology)	
 
Repeat LFT within 48 hours
 
If elevation persists, establish causality
 
Complete liver CRF
 
	
Investigator discretion
 
Monitor LFT within 1 to 4 weeks or at next visit

TBL (isolated)		
> 2 × ULN (in the absence of known Gilbert syndrome)	
 
Repeat LFT within 48 hours
 
If elevation persists, discontinue the study drug immediately
 
Hospitalize if clinically appropriate
 
Establish causality
 
Complete liver CRF
 
	
ALT, AST, TBL, Alb, PT/INR, ALP and γGT until resolutionc (frequency at investigator discretion)
 
Test for hemolysis (e.g. reticulocytes, haptoglobin, unconjugated [indirect] bilirubin)

> 1.5 to ≤ 2 × ULN (patient is asymptomatic)	
 
Repeat LFT within the next week
 
If elevation is confirmed, initiate close observation of the patient
 
	
Investigator discretion
 
Monitor LFT within 1 to 4 weeks or at next visit

Jaundice	
 
Discontinue the study drug immediately
 
Hospitalize the patient
 
Establish causality
 
Complete liver CRF
 
	
ALT, AST, TBL, Alb, PT/INR, ALP and γGT until resolutionc (frequency at investigator discretion)

Any AE potentially indicative of a liver toxicity*	
 
Consider study drug interruption or discontinuation
 
Hospitalization if clinically appropriate
 
Establish causality
 
Complete liver CRF
 
	
Investigator discretion

\*These events cover the following: hepatic failure, fibrosis and cirrhosis, and other liver damage-related conditions; the non-infectious hepatitis; the benign, malignant and unspecified liver neoplasms

a Elevated ALT/AST > 3 × ULN and TBL > 2 × ULN but without notable increase in ALP to > 2 × ULN

b (General) malaise, fatigue, abdominal pain, nausea, or vomiting, or rash with eosinophilia

c Resolution is defined as an outcome of one of the following: (1) return to baseline values, (2) stable values at three subsequent monitoring visits at least 2 weeks apart, (3) remain at elevated level after a maximum of 6 months, (4) liver transplantation, and (5) death.

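### Table 9-2 orders an immediate stop for five liver criteria, but the mandatory list in Section 7.1 has only three of them and Section 9.3 never points to Table 9-2

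*Protocol*

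**What the plan says.** Section 7.1 introduces a mandatory list: "Study treatment must be discontinued under any of the following circumstances". Its liver entries are three: "Elevated AST or ALT > 8x above the ULN"; AST or ALT above 3 times ULN with total bilirubin above 2 times ULN and no ALP rise above 2 times ULN; and AST or ALT above 3 times ULN with listed symptoms. The section also obliges the investigator to stop when continuing is judged harmful on balance.

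Section 9.3 gives a short list of steps for liver events. One is "Discontinuation of the investigational drug (refer to" Section 7.1, with the rider that this applies if appropriate. The section says that the steps are a summary and that the detail is in Table 9-1.

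Table 9-1 holds definitions only. Among the liver events it lists "ALT or AST > 3 x ULN and INR > 1.5" and clinical jaundice. The required actions are in Table 9-2. For isolated bilirubin above 2 times ULN, that table asks for a repeat test within 48 hours and then says "If elevation persists, discontinue the study drug immediately". For ALT or AST above 5 and up to 8 times ULN, it asks for discontinuation if the elevation lasts "more than 2 weeks".

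Treatment is one administration (Section 6.2: "Single dose of CLR 325 (i.v") given over 18 hours (Section 2.1: "To determine the safety and tolerability of an 18-hour i.v. infusion of CLR325 in stable heart failure patients").

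**The concern.** Two parts of one protocol tell the site when to stop the drug for a liver finding, and the lists differ. The section that connects them sends the reader to the shorter list and gives the wrong table number for the detail. The primary objective is safety and tolerability, so stopping instructions should read the same wherever a site looks them up. At stake is the handling of an individual patient during the infusion: two sites with the same finding could act differently, and each could cite the protocol.

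The 2-week row raises a second, smaller question: whether the table was fitted to a treatment that is over in 18 hours.

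**Working it through.** The plan states no figure to reproduce. The check is a comparison of lists, a trace of the pointers and a comparison of time scales.

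**Step 1. Stop actions in Table 9-2 against the list in 7.1**

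| Table 9-2 criterion | Table 9-2 action | In 7.1? |
|---|---|---|
| Potential Hy's Law case | Stop immediately | Yes |
| ALT/AST > 8 x ULN | Stop immediately | Yes |
| ALT/AST > 3 x ULN with symptoms | Stop immediately | Yes |
| ALT/AST > 3 x ULN with INR > 1.5 | Stop immediately | No |
| Jaundice | Stop immediately | No |
| Isolated bilirubin > 2 x ULN | Stop if it persists on repeat | No |
| ALT/AST > 5 to 8 x ULN | Stop if it persists beyond 2 weeks | No |

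Immediate stops: 5 in Table 9-2, 3 in 7.1, so 5 - 3 = 2 are absent. Conditional stops: 2 in Table 9-2, none in 7.1.

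**Step 2. Pointers.** A reader of 9.3 with a liver event is sent to 7.1 for discontinuation and to Table 9-1 for detail. Section 7.1 lacks the two immediate stops, and Table 9-1 contains no actions. The running text of 9.3 does not cite Table 9-2, although the table sits in that section. No sentence says that the lists are cumulative or which one governs.

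**Step 3. Can the missing triggers arise while drug is running?** Table 8-1 schedules blood chemistry at 6, 12 and 18 hours and coagulation at 12 hours.

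- Chemistry at 6 hours leaves 18 - 6 = 12 hours of infusion.
- Chemistry and INR at 12 hours leave 18 - 12 = 6 hours.
- Jaundice is a clinical finding and needs no laboratory result.

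The laboratory triggers can therefore matter during the infusion if results return before hour 18. The protocol gives no turnaround time, and Section 10.3 says that selected samples are processed centrally, so this is an assumption.

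**Step 4. The 2-week row.** 2 weeks = 14 x 24 = 336 hours, and 336 / 18 = 18.7 infusion lengths. Timed from the start of infusion, the condition is met no earlier than 336 - 18 = 318 hours after the drug has ended. For an elevation that first appears after dosing starts, this stop can never be applied.

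**Step 5. The 48-hour repeat.** This is an upper limit. A bilirubin rise at 6 hours is tested again on schedule at 12 hours, so this row can act during the infusion, again if results return in time.

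**The case against.** The strongest reply is that nothing here is a flat contradiction. Section 7.1 does not call its list complete, and no text tells a site to go on dosing when Table 9-2 says stop. A site satisfies both by stopping whenever either says so. The pointer in 9.3 carries the rider about appropriateness, and its steps are described as a summary. Table 9-2 has a column of required actions. Section 7.1 also requires stopping on the investigator's judgement, and Section 6.3 allows it for any safety concern.

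Most of this stands, and it limits the point to what a site could do. It does not remove the point: stopping on judgement is not the same instruction as an unconditional immediate stop, and the additive reading has to be supplied by the reader.

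It is also fair that the 2-week row harms nobody. Once the drug has ended, its stop is merely empty.

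A reader might infer three stronger things:

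- **That a site using 7.1 would continue the infusion.** The judgement clause and the additive reading rule out that certainty.
- **That the row with a repeat within 48 hours cannot operate during the infusion.** The scheduled chemistry draws show that it can.
- **That the study-level pausing rule in Section 7.4 is affected because it depends on the 7.1 list.** That rule counts infusions actually discontinued for safety or tolerability, whichever section prompted the stop, and it does not refer to 7.1.

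**Conclusion.** The point holds as an inconsistency in mandatory safety instructions. Two of the five immediate liver stops in Table 9-2 are absent from 7.1, as is the conditional stop for persistent isolated bilirubin. Section 9.3 sends the reader to the shorter list and misnumbers the table that holds the actions. One further Table 9-2 stop, the 2-week row, cannot act on this treatment.

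The consequence is that a site could continue an infusion that Table 9-2 says to stop. This rests on a site following the written pointers without adding the table and, for the laboratory triggers, on results returning before hour 18. The protocol gives no event frequency, so none is claimed. No sample size, estimate or test depends on the point. It should be corrected, but it is modest in size. Which stopping criteria are clinically right is not judged here.

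**What to change.** Reconcile Section 7.1, Section 9.3 and Table 9-2 so that they give the same list of liver stops, or state which one governs and whether the lists are cumulative. Correct the reference in 9.3 so that the detail of actions points to Table 9-2. Mark each Table 9-2 row as governing the running infusion, follow-up after it, or both; this also settles the 2-week row. The sponsor's medical team decides which criteria belong in the list.

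The cost is amendment wording only, with no change to assessments, sample size or analysis.

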**Table 9-1 Liver Event and Laboratory Trigger Definitions**

	Definition/ threshold
Liver laboratory triggers	3 x ULN < ALT / AST < 5 x ULN 1.5 x ULN < TBL < 2 x ULN
Liver events	ALT or AST > 5 x ULN ALP > 2 x ULN (in the absence of known bone pathology) TBL > 2 x ULN (in the absence of known Gilbert syndrome) ALT or AST > 3 x ULN and INR > 1.5 Potential Hy’s Law cases (defined as ALT or AST > 3 x ULN and TBL > 2 x ULN [mainly conjugated fraction] without notable increase in ALP to > 2 x ULN) Any clinical event of jaundice (or equivalent term) ALT or AST > 3 x ULN accompanied by (general) malaise, fatigue, abdominal pain, nausea, or vomiting, or rash with eosinophilia Any adverse event potentially indicative of a liver toxicity *

**Table 9-2 Follow Up Requirements for Liver Events and Laboratory Triggers**

Criteria	Actions required	Follow-up monitoring
Potential Hy's Law case a	
 
Discontinue the study drug immediately
 
Hospitalize, if clinically appropriate
 
Establish causality
 
Complete liver CRF
 
	ALT, AST, TBL, Alb, PT/INR, ALP and $\gamma$ GT until resolution c (frequency at investigator discretion)
ALT or AST		
> 8 × ULN	
 
Discontinue the study drug immediately
 
Hospitalize if clinically appropriate
 
Establish causality
 
Complete liver CRF
 
	ALT, AST, TBL, Alb, PT/INR, ALP and $\gamma$ GT until resolution c (frequency at investigator discretion)
> 3 × ULN and INR > 1.5	
 
Discontinue the study drug immediately
 
Hospitalize, if clinically appropriate
 
Establish causality
 
Complete liver CRF
 
	ALT, AST, TBL, Alb, PT/INR, ALP and $\gamma$ GT until resolution c (frequency at investigator discretion)
> 5 to ≤ 8 × ULN	
 
Repeat LFT within 48 hours
 
If elevation persists, continue follow-up monitoring
 
If elevation persists for more than 2 weeks, discontinue the study drug
 
Establish causality
 
Complete liver CRF
 
	ALT, AST, TBL, Alb, PT/INR, ALP and $\gamma$ GT until resolution c (frequency at investigator discretion)
> 3 × ULN accompanied by symptoms b	
 
Discontinue the study drug immediately
 
Hospitalize if clinically appropriate
 
Establish causality
 
Complete liver CRF
 
	ALT, AST, TBL, Alb, PT/INR, ALP and $\gamma$ GT until resolution c (frequency at investigator discretion)
> 3 to ≤ 5 × ULN (patient is asymptomatic)	
 
Repeat LFT within the next week
 
If elevation is confirmed, initiate close observation of the patient
 
	Investigator discretion Monitor LFT within 1 to 4 weeks

Criteria	Actions required	Follow-up monitoring
ALP (isolated)		
> 2 × ULN (in the absence of known bone pathology)	
 
Repeat LFT within 48 hours
 
If elevation persists, establish causality
 
Complete liver CRF
 
	
Investigator discretion
 
Monitor LFT within 1 to 4 weeks or at next visit

TBL (isolated)		
> 2 × ULN (in the absence of known Gilbert syndrome)	
 
Repeat LFT within 48 hours
 
If elevation persists, discontinue the study drug immediately
 
Hospitalize if clinically appropriate
 
Establish causality
 
Complete liver CRF
 
	
ALT, AST, TBL, Alb, PT/INR, ALP and γGT until resolutionc (frequency at investigator discretion)
 
Test for hemolysis (e.g. reticulocytes, haptoglobin, unconjugated [indirect] bilirubin)

> 1.5 to ≤ 2 × ULN (patient is asymptomatic)	
 
Repeat LFT within the next week
 
If elevation is confirmed, initiate close observation of the patient
 
	
Investigator discretion
 
Monitor LFT within 1 to 4 weeks or at next visit

Jaundice	
 
Discontinue the study drug immediately
 
Hospitalize the patient
 
Establish causality
 
Complete liver CRF
 
	
ALT, AST, TBL, Alb, PT/INR, ALP and γGT until resolutionc (frequency at investigator discretion)

Any AE potentially indicative of a liver toxicity*	
 
Consider study drug interruption or discontinuation
 
Hospitalization if clinically appropriate
 
Establish causality
 
Complete liver CRF
 
	
Investigator discretion

\*These events cover the following: hepatic failure, fibrosis and cirrhosis, and other liver damage-related conditions; the non-infectious hepatitis; the benign, malignant and unspecified liver neoplasms

a Elevated ALT/AST > 3 × ULN and TBL > 2 × ULN but without notable increase in ALP to > 2 × ULN

b (General) malaise, fatigue, abdominal pain, nausea, or vomiting, or rash with eosinophilia

c Resolution is defined as an outcome of one of the following: (1) return to baseline values, (2) stable values at three subsequent monitoring visits at least 2 weeks apart, (3) remain at elevated level after a maximum of 6 months, (4) liver transplantation, and (5) death.

